After completing the Escalation Part 1 and based on the safety results, we will initiate an expanded cohort, Expansion Part 2 including a total of 19 patients with advanced metastatic CCRCC, to be treated with SLM 4000 in combination with axitinib 5 mg PO BID.

Up to 20 patients in the Expansion Part 2 and pilot phase will have mandatory biopsies at baseline before the start of SLM that will be repeated around day 14 (+/- 3 days) after starting SLM, at Cycle 3 (8 weeks +/- 3 days after first dose of SLM plus Axitinib) and preferably at disease progression, preferably from the same site of the previous biopsy, to study the expression of HIF-a and VEGF by immunohistochemistry (IHC), along with other biomarkers detailed in the correlative studies, before and after treatment with SLM. These tissues will be flash frozen and stored at -80 C to be processed later all at once for the proposed biomarkers.

The candidate patients for the biopsies will be chosen carefully by the treating oncologist and after discussion with the interventional/ body radiologist. Decision will be based on safety, ease of accessibility, tumor size and feasibility of getting the biopsy which can be done either on the primary renal tumor or metastatic site. Patient has to agree to get the biopsies, and sign consent form, after discussing the risks and benefits of the procedure with the provider.

All patients will have a peripheral blood draw at baseline before the start of SLM and repeated on day 14 after starting treatment. This blood will be stored and may be used later to study the protein expression of HIF1a, HIF2a, VEGF and level of SLM.

For Escalation Subjects: All patients will have a peripheral blood draw at baseline before the start of SLM and repeated on day 14 after starting treatment.

For Expansion Subjects: the peripheral blood draw will occur pre-dose and 2 hours post dosing on day 1 then 2 hours post dosing on Day 14 and at Cycles 2, 3, 4, 7, 10 and 13.

Pilot Phase: BSA based dosing. See additional details in protocol Section 14.4.

5.2

STUDY AGENT ADMINISTRATION

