14.3.2 Analysis of secondary endpoint

- a) The expression levels of HIF1a, HIF2a, VEGF and their associated micro-RNAs 210, 155, and LET7b will be evaluated to check if any is altered at each of the dose levels administered.
- b) The following will be provided for the treatment combination:
 - Point estimate of median PFS time and 95% confidence interval by Kaplan-Meier along with survival plots.
 - Point estimate along with 95% confidence interval of the objective response rate (defined as SD+PR+CR, estimated).
 - Point estimate along with 95% confidence interval of the overall survival (OS).

14.4 SAMPLE SIZE AND POWER:

The number of patients to be enrolled in the Escalation Part 1 will depend upon the observed safety profile. The minimum number of patients required is 6 and the maximum is 12.

Of greatest interest for the expansion part 2 is to assess the progression free survival (PFS) for patients treated the dose of SLM in combination with a standard dose of axitinib in advance metastatic CCRCC. Historic median survival for patients within similar subgroup of advanced metastatic CCRCC is reported in the literature to be around 8 months. The goal of the pilot is to have a firsthand rough estimate of the median survival in our study population and define hypotheses for a subsequent larger trial.

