20.0 SLM STUDY LAB CALENDAR ESCALATION SUBJECTS (BASED ON V9 PROTOCOL)

Test	Day 1	Day 14 (Cycle 1)	C2 (Day 1)	C3	C4	C5	C6	C7	C10	C13
SLM (3 ml purple tube)	Pre & Post 2 Hours	Pre & Post 2 Hours	Pre & Post 2 Hours	Post 2 Hours	Post 2 Hours	Pre & Post 2 Hours	Post 2 Hours	Pre & Post 2 Hours	Post 2 Hours	Post 2 Hours
miRNA (6ml purple tube)	Pre	Pre								
Biomarkers (6 ml pink tube)	Pre	Pre	Post 2 Hours	Post 2 Hours	Post 2 Hours	Post 2 Hours	Post 2 Hours	Post 2 Hours	Post 2 Hours	

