20.1 SLM STUDY LAB CALENDAR EXPANSION SUBJECTS

Test	D1	D14	C2	C3	C4	C7	C10
SLM (3 ML purple tube)	Pre and 2 hour post	2 hr post only					
miRNA (6 ml purple tube)	Pre	2 hr post only					
Biomarkers (6 ml pink tube)	Pre	2 hr post only					

20.2 20.2 SLM STUDY LAB CALENDAR PILOT SUBJECTS

Test	D1	D14	C2	C3	C4	C7	C10	C13
SLM (3 ML purple tube)	Pre	2 hr post only	X	X	X	X	X	X
miRNA (6 ml purple tube)	Pre	2 hr post only						
Biomarkers (6 ml pink tube)	Pre	2 hr post only	X	X	X	X	X	X

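### Day 14 blood for miRNA and biomarkers is drawn pre-dose in escalation but 2 hours post-dose in expansion and pilot, always against a pre-dose Day 1 baseline, so the blood-marker change does not measure the same thing in every phase

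*Combined protocol and SAP*

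**What the plan says.** Footnote 8 of the study calendar (Section 11.0) sends escalation, expansion and pilot patients to lab calendars 20.0, 20.1 and 20.2 respectively, so those tables govern sampling by phase.

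- **Escalation (20.0).** The Day 1 and Day 14 entries are "miRNA (6ml purple tube) Pre Pre" for miRNA. The biomarker row begins "Biomarkers (6 ml pink tube) Pre Pre Post 2 Hours", so it moves to 2 hours post-dose only from Cycle 2.
- **Expansion (20.1).** The rows are "miRNA (6 ml purple tube) Pre 2 hr post only" and "Biomarkers (6 ml pink tube) Pre 2 hr post only". The selenium row alone has a 2-hour Day 1 sample: "SLM (3 ML purple tube) Pre and 2 hour post 2 hr post only".
- **Pilot (20.2).** The miRNA and biomarker rows have the same Day 1 and Day 14 entries as in 20.1. No tube has a 2-hour Day 1 sample.
- **Section 5.1, expansion.** One sentence covers the blood draw as a whole: "the peripheral blood draw will occur pre-dose and 2 hours post dosing on day 1 then 2 hours post dosing on Day 14".
- **Section 14.3.2(a).** HIF1a, HIF2a, VEGF and miRNA 210, 155 and LET7b "will be evaluated to check if any is altered at each of the dose levels administered". Sampling time is not mentioned and no test is named.

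Section 10.1 makes blood, as well as tissue, a source for the miRNAs. Section 5.1 makes use of stored blood for HIF and VEGF protein a later option.

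**The concern.** A change from baseline is easiest to interpret when both samples are taken under the same conditions. Escalation meets that condition for these tubes. Expansion and pilot do not: their Day 14 sample follows a dose by 2 hours and their Day 1 sample precedes the first dose. The difference between the two contains whatever 14 days of selenomethionine has done, plus whatever a single dose, a meal or two hours of clock time does.

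Secondary objective 4 asks whether the administered dose is enough to alter these markers, and 14.3.2(a) answers it by dose level. Fresh biopsies are confined to expansion and pilot, in up to 20 patients. For the fixed 2500 and 3000 mcg levels, blood is therefore the only planned source of an on-treatment change. A reader who sets those levels beside 4000 mcg would be looking at two sampling schemes as well as different doses.

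**Working it through.** **Step 1. Schedules side by side (miRNA and biomarker tubes).**

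| Phase | Calendar | Day 1 | Day 14 | Time-matched Day 1 sample? |
|---|---|---|---|---|
| Escalation | 20.0 | pre | pre | yes |
| Expansion | 20.1 | pre | 2 h post | no |
| Pilot | 20.2 | pre | 2 h post | no |

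Calendar 20.0 labels its column Day 14 (Cycle 1). I read this as Day 14 of the run-in, as in the other two calendars.

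**Step 2. What the change estimates.** Let D be the sustained 14-day effect and a the shift between a pre-dose and a 2-hour sample, both in SD of the change.

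- Escalation: expected change = D.
- Expansion and pilot: expected change = D + a.

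Without a second sample, D and a cannot be separated in the last two phases. If a = 0 there is no bias. The documents give no value for a.

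**Step 3. How the schemes map to dose.** Section 2.3 lists fixed-dose cohorts C1 to C4 at 4000, 2500, 3000 and 4000 mcg. Section 5.1 puts 19 expansion patients at 4000. Assume 3 patients per escalation cohort. The documents do not say which phase C4 belongs to, so both cases are shown.

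- Fixed 2500 and 3000 mcg: 0% post-dose on Day 14.
- Fixed 4000 mcg, C1 and C4 both escalation: 19/(19 + 6) = 19/25 = 76% post-dose.
- Fixed 4000 mcg, only C1 escalation: 19/(19 + 3) = 19/22 = 86% post-dose.
- Pilot: 100% post-dose.

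With D = 0 everywhere, the apparent difference between 4000 mcg and the two lower fixed doses is a times that share:

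| Assumed a (SD) | Share 0.76 | Share 0.864 |
|---|---|---|
| 0.25 | 0.19 | 0.22 |
| 0.50 | 0.38 | 0.43 |

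**Step 4. Illustration within expansion.** The plan has no marker test to reproduce. As a yardstick, take a two-sided 5% paired t-test with n = 19 and D = 0. The critical value is t(0.975, 18) = 2.101 and the non-centrality is a × √19. Rejection probability is the non-central t area beyond ±2.101.

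| Assumed a (SD) | a × √19 | Rejection rate |
|---|---|---|
| 0 | 0 | 5% |
| 0.10 | 0.436 | 7.0% |
| 0.25 | 1.090 | 17.8% |
| 0.50 | 2.179 | 54.1% |

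The same formula for all 10 pilot patients together gives 6%, 11% and 29% for the three non-zero shifts.

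**Step 5. Section 5.1 against 20.1.** Read alone, the 5.1 sentence provides both a pre-dose and a 2-hour Day 1 draw, which would supply a matched baseline. Calendar 20.1 restricts the 2-hour Day 1 sample to the selenium tube. The gap therefore shows in the calendars, and the two places disagree about what was to be collected.

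**The case against.** **No between-dose comparison is planned.** Section 14.3.2(a) asks a within-level question and specifies no dose-response model, pooling or test. A reader might infer that the plan contains a dose comparison that sampling time invalidates; it does not. What stands is that the within-level summary at fixed 4000 mcg already mixes two schemes, and that nothing warns against reading across levels.

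**Larger error rates are tempting.** Pooling expansion and pilot (n = 29) would give a 74% rejection rate at a 0.50 SD shift. That pools dose levels the plan evaluates separately, uses a test it does not name and rests on an assumed shift. The n = 19 figures correspond to expansion, but the test and shifts behind them are equally assumed.

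**A post-dose shift may be a drug effect.** The objective does not require a trough effect, so a marker that moves 2 hours after a dose has still been altered by selenomethionine. This stands. The problem is interpretation: acute and sustained effects, and any food or clock-time effect, cannot be told apart.

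**One more dose may add little by Day 14.** In Section 2.3, cohort 1 selenium rises from 2.1 to 30.0 over about 28 doses: (30.0 − 2.1)/28 ≈ 1.0 per dose, about 3% of the Day 14 level. This favours a small shift, but it ignores any absorption peak and concerns selenium, not the markers.

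**HIF and VEGF are mainly read in tissue.** Correct. Biopsy immunohistochemistry and tissue miRNA are untouched, and blood HIF/VEGF is optional. The documents do not support saying that the sampling times would produce a false VEGF finding.

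Part of the lab manual (Section 19.0) was not available for this review; any tube timing given there should be checked.

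**Conclusion.** The concern holds in a limited form. The governing calendars use two sampling schemes for blood miRNA and biomarkers, split by phase, and expansion and pilot have no time-matched marker baseline in those calendars. Their Day 1 to 14 change cannot isolate a sustained effect. The fixed 4000 mcg level is a mixture, 76% to 86% post-dose if escalation cohorts have 3 patients each.

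Whether this produces material bias is unknown. It depends on a 2-hour or time-of-day shift that the documents neither report nor rule out, and the rejection rates above are illustrations only. The main exposure is blood miRNA, a secondary objective. Escalation levels remain comparable with one another for these tubes, since all were sampled pre-dose on both days. Selenium concentration is less affected, because escalation also has a 2-hour Day 14 selenium sample.

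**What to change.** 1. **Section 14.3.2(a).** Add: *Day 1 to 14 change in blood markers will be summarised separately by sampling scheme (pre/pre for escalation; pre/2-hour post for expansion and pilot). The schemes will not be combined within 4000 mcg, and differences across schemes will not be read as dose effects.* State the limitation in the report. Cost: a short text change.
2. **Sections 5.1 and 20.1.** Reconcile them on which expansion tubes were to be drawn 2 hours after the Day 1 dose. If any marker blood from that time exists, use it as the time-matched baseline. Cost: a check of sample records.
3. **Calendar 20.2.** For any pilot patient not yet at Day 14, add pre-dose Day 14 miRNA and biomarker tubes and keep the 2-hour tubes. Replacing the 2-hour marker tubes would split a 10-patient cohort between schemes and lose the match with expansion; adding tubes gives both the like-for-like change and that match. The 2-hour selenium sample stays, so the Day 14 concentration used by the continual reassessment method is unchanged. Cost: one extra small draw at a visit already held.

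Escalation is complete and expansion enrolment has closed, so for those phases the remedy lies in analysis and reporting.

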5.3 SLM AND AXITINIB ADMINISTRATION

SLM oral capsules will be given twice daily alone for the first 14 days, then once daily in combination with Axitinib thereafter. SLM dosing will be based on patient BSA for the Pilot phase and tolerance based on DLT assessments during run-in only. See section 14.4 for dosing information for the Pilot portion. SLM will be provided by the study free of charge, by Sabisna Corporation located in NJ, USA. SLM will be stored in the Investigational Pharmacy at University of Iowa Hospitals and Clinics.

Axitinib oral tablets will be provided by the study free of charge from Pfizer and stored in the Investigational Pharmacy at the University of Iowa Hospitals and Clinics. Dosing will start at 5 mg twice daily, with the two doses taken 12 hours apart, with or without food. Axitinib will begin after the patient completes the 14 day SLM run-in portion of the trial.

Over the course of treatment, patients who tolerate Axitinib for at least two consecutive weeks with no adverse reactions >Grade 2 (according to the Common Toxicity Criteria for Adverse Events [CTCAE]) may have their dose increased as follows.

When a dose increase from 5 mg twice daily is recommended, the Axitinib dose may be increased to 7 mg twice daily, and further to 10 mg twice daily using the same criteria.

5.4 GENERAL CONCOMITANT MEDICATION AND SUPPORTIVE CARE GUIDELINES

No premedication will be recommended. All standard of care antiemetics, antidiarrheals, or antibiotics are permitted if clinically indicated. During the course of treatment, if there is a need for palliative intervention such as radiation therapy or surgery, subjects are allowed to stay on study, and it will be to the discretion of the treating provider and study PI whether to continue or hold study combinations drug. Treating physician will take into consideration, safety and toxicity of the procedure and the patient's best interest.

5.5 DURATION OF FOLLOW-UP

Patients will be followed up, until they are lost to follow-up or death, whichever occurs first. Patients removed from study for unacceptable adverse event(s) will be followed for resolution or stabilization of the adverse event as well. Follow up off study will be performed using telephone contact correspondence with treating physicians, and death records as necessary to update vital status at least every 6 months.

5.6 EVALUATIONS DURING SCREENING AND TREATMENT:

The following evaluations and assessments will be performed at the specified times listed in the study calendar (section 11.0):

- Physical examination
- Vital signs including blood pressure with each visit
- Assessment of ECOG performance status
- Clinical Chemistries
- CBC with differential
- Urinalysis
- Glucose
- Erythropoietin levels
- Lipid Panel
- Coagulation levels
- Blood sample(s) for SLM concentration analysis, miRNA samples and additional blood for storage.
- Pregnancy test for women of childbearing potential.
- EKG
- Dual Energy CT Scans will occur at Screening, Day 14 and Cycle 3(8 weeks after first dose of SLM plus Axitinib)
- Disease assessments CT +/- Bone Scan will begin at Cycle 5 Day 1(every 8 weeks +/- 5 days). These scans will be performed as determined by the treating physician. If subject is asymptomatic, bone scans may be done every 4 months.
- Concomitant medications
- All treatment-related adverse events should be followed until resolution or stabilization.
- Safety phone call to assess subject status. Archival tumor tissue collection, if availableFresh Tumor Tissue Biopsy at Screening, Day 14 and Cycle 3 (+/- 3 days both occasions) and preferable at progression, for up to 20 patients in Expansion Phase and the Pilot phase, if accessible and deemed safe by physician.

5.6.1 CRITERIA FOR REMOVAL FROM STUDY

Patients will continue study treatment until any of the following occur:

- Disease progression (treatment beyond progression at the discretion of treating provider with confirmatory scan in 8 weeks if the patient is clinically doing well).
- Unacceptable toxicity
- Intercurrent illness that prevents further safe administration of treatment
- Withdrawal of consent
- Serious protocol violation
- Non-compliance to therapy regimen
- General or specific changes in the patient's condition rendering the patient unacceptable for further treatment, in the judgment of the investigator

The reason for study removal and the date the patient was removed must be documented on the Case Report Form.

5.7 END OF TREATMENT:

The end-of-treatment visit is to be conducted 28 days (+/- 7 days) after treatment discontinuation, and will include the following assessments:

- Physical examination
- Vital signs including blood pressure
- Assessment of ECOG performance status
- Clinical Chemistries
- CBC with differential
- Glucose
- Urinalysis
- Assessment of adverse events
- Concomitant medications
- Mandatory Fresh Tumor Tissue Biopsy at disease progression, for up to 20 patients in Expansion and pilot Phase, if accessible and deemed safe by physician.

5.8 EVALUABLE POPULATIONS:

For Escalation Part 1: the DLT evaluable population includes all patients who complete one cycle of SLM and patients who experience a DLT during the first cycle of dosing.

For Escalation Part 1 and Expansion Part 2: The safety population includes all patients who receive at least one dose of SLM.

For Expansion and Pilot Phase: The evaluable population includes all patients who have measurable disease at screening, according to RECIST criteria for the relapsed solid tumor cohort and undergo a baseline disease assessment and at least one on-treatment disease assessment. Evidence of disease progression including radiological assessments, hematological assessments, death due to disease progression, and study drug withdrawal due to disease progression will be counted as post-baseline disease assessments. Evaluation for clinical response will include only those with measurable disease at baseline and evaluation of progression will be evaluated in all patients regardless of measurable disease status at baseline.

6.0 SAFETY ASSESSMENTS:

- A urinalysis for protein will be performed before starting axitinib and monthly while on it, and if more than 2+ is detected, urine protein to creatinine (UPC) ratio is to be determined (or 24 hour urine protein excretion).
- Blood pressure will be measured with every office visit, patient will be asked to keep a diary with daily record of blood pressure at home. Development of a hypertensive crisis will mandate discontinuation of the drug.
- Hematology and biochemistry will be assessed each clinic visit.
- Physical examination and vital signs will be assessed at baseline and with each clinic visit.

7.0 DOSING DELAYS/ DOSE MODIFICATIONS

Adverse Event	Action with Axitinib	Action with SLM
DLT during Run-in (see section 14.4)	NA	Permanently D/C Treatment
Grade 4 Hematologic (not controlled by standard supportive care)	Hold drug until resolved to grade 1*; restart at same dose level; if same grade 3 event re-occurs then hold until resolved to grade 1* and reduce drug as noted below**	Hold drug until resolved to grade 1*. No dose reductions.
Grade 3-4 Non-hematologic (not controlled by standard supportive care)	Hold drug until resolved to grade 1*; restart at same dose level; if same grade 3 event re-occurs then hold until resolved to grade 1* and reduce drug as noted below**	Hold drug until resolved to grade 1*. No dose reductions.
Grade 2 weight loss	Continue drug but consider dose reduction**	Continue treatment
Proteinuria > 2+ with urine protein creatinine (UPC) ratio 2.0 or greater, or 24 hour urine protein is >2 grams	Hold and repeat urine creatinine protein ratio or 24hr urine in 1 week. Resume treatment when ratio < 2.0 or under 2g/24hr; If protein >3.5g/24, hold drug and repeat 24 hr urine and creatinine clearance weekly. May resume when under 2g/24hr. Consider dose reduction if event re-occurs.	Continue treatment
Hypertension >150 systolic or >90 diastolic which is recurrent or persistent after maximum antihypertensive treatment	Interrupt until <150 systolic and <90 diastolic and reduce dose as noted below**	Continue treatment

*If patient's baseline value is > grade 1, then interruptions should resolve to baseline value or grade 1 whichever is appropriate for the patient.

**If dose reduction from 5mg twice daily is required, the recommended dose is 3mg twice daily. If additional reduction is required, the recommended dose is 2mg twice daily.

7.1 GENERAL GUIDELINES:

Patients who cannot resume treatment within 6 weeks due to persistent toxicities should be withdrawn from the study.

Axitinib dose can be re-escalated after symptoms improve to grade 1 and per provider discretion.

Over the course of treatment, management of some adverse drug reactions may require temporary interruption up to one week of one or both drugs per the provider discretion and after discussion with patient even if the symptoms are not grade 3/4. From previous experience in the dose escalation phase, both patients and provider found these periodic interruptions to be helpful for the patient quality of life.

Management of some adverse drug reactions may require temporary interruption or permanent discontinuation and/or dose reduction of axitinib therapy. If dose reduction from 5 mg twice daily is required, the recommended dose is 3 mg twice daily. If additional dose reduction is required, the recommended dose is 2 mg twice daily.

Patients who develop progressive disease will be off-study but will continue to be followed for survival. For equivocal findings of progression (e.g. very small and uncertain new lesions; cystic changes or necrosis in existing lesions), treatment may continue until the next scheduled assessment. If at the next scheduled assessment, progression is confirmed, the date of progression should be the earlier date when progression was suspected.

If 10% or more of the patients evaluated cumulatively every 3 months have a toxic adverse event of grade 3 or higher that was attributable to the investigational agents and that could not be alleviated or controlled within 14 days of starting supportive care, assignment of patients will be suspended until the sponsor and the data and safety monitoring committee (DSMC) have reviewed the events and determined the appropriate course of action.

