Patients will be followed both clinically and radiographically (CT) at baseline then every 8 weeks after starting the treatment. Responses will be assessed using RECIST 1.1 criteria. Dose level 1 (4000 µg) will be the starting dose in the standard 3+3 dose escalation design. Three patients will be recruited for Dose level 1.

The next three patients will be recruited for Dose level -1 (2500 µg). While none of the three patients in Dose level 1 experienced a DLT, there were significant side effects. If 0 of three patients at Dose level -1 experiences a DLT related to SLM, then dose escalation will proceed to the next dose level (3000 µg).

If one of the three patients at Dose level -1 experiences a DLT related to SLM, then three more patients will be treated at the same dose. If exactly one out of six patients experiences a DLT, then dose escalation will proceed to the next dose level (3000 µg) after discussion at the weekly SLM meeting.

If two of the first three patients experience DLT related to SLM, then the dose will de-escalate to the lower dose (1500 µg).

The next patient can be enrolled after the previous patient's 28th Day of SLM assessment, provided there are no DLTs related to SLM. The minimum number of patients required is 6 and the maximum is 12.

Dose Limiting Toxicities:

DLTs related to SLM will be defined as any of the following events determined by the Investigator to be related to treatment combination irrespective of outcome. This applies to the first cycle only (2 weeks SLM alone + 4 weeks combination therapy):

- Clinically significant non-hematologic toxicity of Grade 3 or greater not related to underlying malignancy.
- Severe hematological toxicity (Grade 4 neutropenia, Grade 3-4 febrile neutropenia, or Grade 4 thrombocytopenia).
- If resolution of DLT related to SLM does not occur in 4 weeks, then patient will be withdrawn from the study.
- Grade 4 nausea, vomiting, diarrhea, or electrolyte imbalances or Grade 3 nausea, vomiting, diarrhea and electrolyte imbalances lasting greater than 48 hours despite optimal medical intervention.
- In the dose escalation phase, treatment delays related to the study drug that last >2 weeks

- Any grade 3 or higher DLT related to SLM alone will be discussed at the weekly SLM committee meeting.
-

Expansion Part 2: Enrollment Completed

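### Section 7.0 requires an axitinib reduction when a severe event recurs at Grade 3 but, read literally, not when it recurs at Grade 4

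*Combined protocol and SAP*

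**What the plan says.** Two rows of the table in 7.0 deal with severe toxicity in general. They are headed "Grade 4 Hematologic (not controlled by standard supportive care") and "Grade 3-4 Non-hematologic (not controlled by standard supportive care"). Their axitinib cells are identical. At the first event axitinib is held until it has resolved to grade 1 (or to baseline, under the footnote). The cell then continues: "restart at same dose level; if same grade 3 event re-occurs then hold until resolved to grade 1", followed by an instruction to reduce according to the double-asterisk footnote. That footnote gives recommended reduced doses and contains no trigger of its own.

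In both rows SLM is held and is never reduced, so axitinib is the only drug whose dose these rows can lower.

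Elsewhere, 7.1 says: "Management of some adverse drug reactions may require temporary interruption or permanent discontinuation and/or dose reduction of axitinib therapy". It also says: "Patients who cannot resume treatment within 6 weeks due to persistent toxicities should be withdrawn from the study". Section 5.6.1 lists "Unacceptable toxicity" among the reasons to stop treatment.

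**The concern.** The rule for repeat severe toxicity names one grade, and it is the lower one. A patient whose event returns at Grade 3 must be reduced. A patient whose event returns at Grade 4 meets the row's entry condition again and, on the words alone, is held and restarted at the same dose.

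A provider can still reduce, but that rests on judgment and not on the rule. Monitoring under Appendix B includes compliance with the study plan. A same-dose restart after a repeat Grade 4 event would comply with the text, so a check against the text would not flag it. Characterizing the safety of the combination is a primary objective, and the rule for its worst repeat toxicities should leave no doubt.

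**Working it through.** No arithmetic applies and the plan states no figure to reproduce. The check is to read the two cells against their row headings, and then against every other rule that might require a reduction.

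**Step 1: readings of the trigger.** The words can be taken in three ways.

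| Reading | Hematologic row (entry at Grade 4) | Non-hematologic row (entry at Grade 3 or 4) | Reduction required after a Grade 4 repeat? |
|---|---|---|---|
| A. Strict: first and repeat events both Grade 3 | Never met, because the first event is Grade 4 | Met only by Grade 3 followed by Grade 3 | No |
| B. Same kind of event, repeat at exactly Grade 3 | Met by a Grade 3 repeat | Met by a Grade 3 repeat after either grade | No |
| C. Probable intent: repeat at Grade 3 or above | Met by a Grade 3 or 4 repeat | Met by a Grade 3 or 4 repeat | Yes |

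A and B follow the words, and neither reaches a Grade 4 repeat. Only C does, and C has to be supplied by the reader.

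**Step 2: the hematologic row.** Its entry grade is 4 and its trigger grade is 3. Under A the trigger cannot be met. Under B a Grade 3 recurrence forces a hold and a reduction, although Grade 3 hematologic toxicity does not enter the row. Either way trigger and entry do not match, which points to text shared between two rows with different entry grades.

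**Step 3: how the protocol writes Grade 3 and above elsewhere.**
- The DLT list in 5.1: "Clinically significant non-hematologic toxicity of Grade 3 or greater not related to underlying malignancy".
- The suspension rule in 7.1, for patients who "have a toxic adverse event of grade 3 or higher that was attributable to the investigational agents".
- The non-hematologic row heading itself, which names both grades.

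The protocol therefore has wording for this and does not use it in the two cells.

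**Step 4: other rules that might require the reduction.**
- The 7.1 sentence on managing adverse reactions is permissive and has no grade trigger.
- The 6-week rule applies only when treatment cannot be resumed.
- The stopping criterion in 5.6.1 gives no grade or recurrence rule.
- The 10% rule in 7.1 suspends assignment of patients; it does not set the dose of a treated patient.
- The hypertension row requires interruption and reduction without a grade trigger, section 6.0 makes a hypertensive crisis a reason to discontinue, and proteinuria has its own row. These events are outside the gap.

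None of these requires an axitinib reduction after a repeat Grade 4 event in the two rows.

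**The case against.** The strongest reply is that no clinician would read the cell this way. The hematologic row cannot be applied word for word in any case, so the reader must interpret it, and the natural interpretation is Grade 3 or above. The drug is still held until the event resolves. The provider may reduce or stop under 7.1 and 5.6.1. Under 7.1 axitinib may also be re-escalated at the provider's discretion once symptoms have improved to grade 1, so even a required reduction need not last. Both rows apply only to events that standard supportive care does not control. Escalation is complete and expansion enrollment is closed.

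Most of this stands, and it limits the consequence. It does not remove the error. The two rows instruct a reduction, whereas the weight-loss and proteinuria rows only ask the provider to consider one. A rule written as an instruction should cover the worse case.

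A reader might infer three stronger points that the documents do not support:
- **That the protocol forbids a reduction after a repeat Grade 4 event, or leaves the patient unprotected.** It does neither. The reduction is allowed but not required.
- **That the gap can be expressed as a share of grade combinations, or as a fixed loss of dose reduction.** Any such share changes between readings A and B, and the footnote's reduced dose is only a recommendation.
- **That missing reduction steps above 5 mg twice daily are part of the defect.** Titration follows the package insert, which the documents do not reproduce in full, so nothing can be concluded on this.

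**Conclusion.** The point holds as a drafting error in an operative safety rule. On either literal reading, the two severe-toxicity rows require no axitinib reduction after a repeat Grade 4 event, and in the hematologic row the trigger does not match the entry grade.

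The reach is small: uncontrolled events in the 10 planned pilot patients and in anyone from the earlier parts still on treatment. The documents do not say how often repeat Grade 4 events occur, so no expected number of affected patients can be given.

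The expansion sample size and power are unaffected. So are the pilot's Day 14 selenium concentration and its Day 1 to 14 DLT window, because axitinib starts only after the 14-day run-in.

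The conclusion rests on two things: that the cell text is as printed, and that the intent was Grade 3 or above. The second is an inference from the protocol's wording elsewhere, which the sponsor should confirm.

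**What to change.** Change the recurrence condition in two axitinib cells of the 7.0 table and leave the rest of each cell as it is.

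- **Non-hematologic row:** *if the same event re-occurs at Grade 3 or higher*, followed by the existing hold and reduction.
- **Hematologic row:** name Grade 4 explicitly. One option is *if the same event re-occurs at Grade 3 or higher*, which keeps Grade 3 as a trigger although it lies below the row's entry grade. The other is *if the same event re-occurs at Grade 4*, which matches the entry grade and drops the Grade 3 trigger. Both close the gap; the sponsor should confirm which is meant.

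The cost is one wording amendment to two cells. It needs no new visits, tests or data and does not change the sample size.
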